#### 5.3. Multicentre Studies

Data will be summarized for all centres combined. The primary efficacy endpoint will be summarized by Country. Countries will be combined if the number of participants enrolled is low.

### 5.4. Examination of Covariates, Other Strata and Subgroups

#### 5.4.1. Covariates and Other Strata

The list of covariates may be used in descriptive summaries. Additional covariates of clinical interest may also be considered.

Category	Details
Strata	None
Covariates	See details in Section 5.4.2

## 5.4.2. Examination of Subgroups

The following is a list of subgroups that may be used in descriptive summaries. Additional subgroups of clinical interest may also be considered.

- If the percentage of subjects is small within a particular subgroup, then the subgroup categories may be combined.
- Additional covariates of clinical interest may also be considered.

Category	Covariates and / or Subgroups
Demographic and Baseline Characteristic Subgroups	
 
Age (years):         
 
35, 35 - <50,≥50
 
≤18, 19 - 64, ≥65 (FDAAA requirement)
 
18 - 64, 65 - 84, ≥85 (EMA requirement)
 
 
 
Race:         
 
White, Non-White
 
Black/African American, Non-Black/African American
 
 
 
Sex at birth:         
 
Female
 
Male
 
 
 
Country:         
 
Canada
 
United States
 
 
 
Derived Baseline Centers for Disease Control and Prevention (CDC) category:             
 
Stage II
 
Stage III
 
Baseline BMI (kg/m²)
 
<30
 
≥30
 
 
 

Additional subgroup for common drug-related study drug injection site reaction (ISR) with maximum toxicity grade	For each preferred term of the common drug-related study drug ISR with maximum toxicity grade (pain, induration, nodules and any other study drug ISR with ≥5% subjects in either treatment arm) during the maintenance phase:  • Needle Length for Last CAB Injection prior to and including the onset date of the earliest corresponding drug-related CAB ISR with maximum toxicity grade during the maintenance phase: ≤1.5, >1.5 to <2, ≥2 inches  • Needle Length for Last RPV Injection prior to and including the onset date of the earliest corresponding drug-related RPV ISR with maximum toxicity grade during the maintenance phase: ≤1.5, >1.5 to <2, ≥2 inches  Note: If there is no ISR of interest reported during maintenance

Category	Covariates and / or Subgroups		
	phase for a subject, the needle length of last injection during		
	maintenance phase will be used in the summary.		

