6.5.1. Dosing Considerations for CAB LA + RPV LA

Vials of CAB LA and RPV LA are each supplied as a suspension and need no further dilution or reconstitution. Since RPV LA requires refrigeration, sites should allow the

vial to come to approximately room temperature prior to injecting. The vials should be gently inverted a few times to re-suspend sediments and allow bubbles to subside, and then use a syringe to withdraw the required volume of suspension for IM injection.

All injections must be given intramuscularly in the gluteus medius. Sites may use their discretion as to where in the gluteus muscle each injection is given according to individual participant circumstance. If possible, injections should be spaced approximately 2 cm from one another, from the site of any previous injection or any injection site reaction. The time and location of injection will be captured in the eCRF.

Intermuscular injections should be administered at a 90-degree angle into the gluteus medius muscle using a needle of appropriate gauge and length (In most participants, a 1.5” 23 gauge needle for CAB LA and a 1.5” 23 gauge needle for RPV LA is recommended). The needle should be long enough to reach the muscle mass and prevent study drug from seeping into subcutaneous tissue, but not so long as to involve underlying nerves, blood vessels, or bone. Variable needle lengths and/or needles with different gauge (CAB LA: 21 to 25 gauge; RPV LA: 21 to 23 gauge) are permitted if needed to accommodate individual body types. Longer needle lengths may be required for participants with higher body mass indexes (BMIs, example > 30), to ensure that injections are administered intramuscularly as opposed to subcutaneously. BMI, needle gauge and length used will be collected in the eCRF. Additional details of the injection device used by sites for IM administration including, but not limited to functional performance, may also be collected within the eCRF.

At the Day 1 visit, participants transitioning from oral CAB + RPV should be dosed with the IM regimen within 2 hours of taking the last oral regimen dose where possible.

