#### 8.1.1. Injection Site Reactions

For the summary of Injection Site Reaction Adverse Events by Visit and Maximum Severity (Overall and by Common ISRs): ISRs will be assigned based on onset date to the most recent planned IM injection visit prior or equal to the AE onset date.

Maximum grade at each visit will be derived as the maximum grade among ISRs assigned to the particular visit, with consideration for whether the summary applies to a particular preferred term (vs. across preferred terms), or drug-related associated to CAB and/or RPV, or stratification by needle length (refer to Section 5.4.2).

Drug-related ISRs (based on investigator discretion) will be attributed to the causal agent (CAB vs. RPV) when this can be determined specifically based the side of injection administration and the side of the reported ISR (as collected in the eCRF). If we are unable to determine the causal agent in those cases where both drugs are given on one side and the ISR is reported non-specifically, then the attribution to a specific causal agent will remain unknown.

Common study drug ISR adverse events are defined by MedDRA preferred terms including injection site pain, injection site induration, injection site nodules and preferred terms of any other ISR with  $\geq$ 5% participants in the CAB LA + RPV LA arm, coming from study drug injections. The same set of common terms will be applied to 'overall' (CAB and/or RPV), CAB alone, RPV alone.

ISRs will be attributed to the needle length ( $\leq 1.5$ , > 1.5 to < 2,  $\geq 2$  inches) when this can be determined specifically based on the side of injection administration and the side of the reported ISR (as collected in the eCRF). If we are unable to determine the needle length in those events where both drugs are given on one side and their needle lengths are different, then the attribution to a needle length will remain unknown.

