3.16.	Safety	207966/primar y_02/T3.62	Summary of Change from Baseline QTc Values by Category		M12, M26, EOS		
Vital S	igns						
3.17.	Safety	VS1	Summary of Change from Baseline in Vital Signs by Visit		M12, M26, EOS		
Study	Drug Injection	Site Reaction A	dverse Events (display for Q2M arm only)				
3.18.	Safety	207966/primar y_02/T3.28	Summary of Study Drug Injection Site Reaction Adverse Events (Event-level Summary)		HL, M12, M26, EOS		
3.19.	Safety	207966/primar y_02/T3.29	Summary of Subject-level Characteristics of Study Drug Injection Site Reaction Adverse Events – Overall and Common		M12, M26, EOS		
3.20.	Safety	207966/primar y_02/T3.30	Summary of Study Drug Injection Site Reaction Adverse Events by Visit and Maximum Severity – Overall and Common	Replace definition of common in the footnote with 'Note: Common ISR includes pain, induration, nodules and any other ISR with >=5% subjects in Q2M treatment arm'	M12, M26, EOS		

Safety	Safety: Tables							
No.	Population	IDSL / Example Shell	Title	Programming Notes	Deliverable			
3.21.	Safety	207966/primar y_02/T3.31	Summary of Drug-related Study Drug Injection Site Reaction Adverse Events (Event-level Summary) – CAB		M12, M26, EOS			
3.22.	Safety	207966/primar y_02/T3.32	Summary of Drug-related Subject-level Characteristics of Study Drug Injection Site Reaction Adverse Events – Overall and Common (CAB)		M12, M26, EOS			
3.23.	Safety	207966/primar y_02/T3.33	Summary of Overall and Common Drug-related Study Drug Injection Site Reaction Adverse Events by Visit and Maximum Severity – CAB		M12, M26, EOS			
3.24.	Safety	207966/primar y_02/T3.34	Summary of Maximum Drug-related Study Drug Injection Site Reaction Adverse Event Grade by Needle Length – Common (CAB)	Replace definition of common in the footnote with 'Note: Common ISR includes pain, induration, nodules and any other ISR with >=5% subjects in Q2M treatment arm'	M12, M26, EOS			
3.25.	Safety	207966/primar y_02/T3.35	Summary of Drug-related Study Drug Injection Site Reaction Adverse Events (Event-level Summary) – RPV		M12, M26, EOS			
3.26.	Safety	207966/primar y_02/T3.36	Summary of Drug-related Subject-level Characteristics of Study Drug Injection Site Reaction Adverse Events – Overall and Common (RPV)		M12, M26, EOS			
3.27.	Safety	207966/primar y_02/T3.37	Summary of Overall and Common Drug-related Study Drug Injection Site Reaction Adverse Events by Visit and Maximum Severity – RPV		M12, M26, EOS			

Safety:	Safety: Tables							

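### The ISR-by-needle-length tables read needle length at a time that depends on the outcome, so they can show spurious differences if needle length changes systematically

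*SAP*

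**What the plan says.** SAP 5.4.2 defines an additional subgroup for common drug-related ISRs, applied to each preferred term. For CAB, a participant with the reaction is classed by the "Needle Length for Last CAB Injection prior to and including the onset date of the earliest corresponding drug-related CAB ISR with maximum toxicity grade" in the maintenance phase; a parallel rule covers RPV. The categories are up to 1.5 inches, above 1.5 to below 2, and 2 or more. A note gives the rule for everyone else. It opens "If there is no ISR of interest reported during maintenance" and goes on "phase for a subject, the needle length of last injection during" the maintenance phase as the value to use.

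The display that matches this subgroup is SAP Table 3.24, "Summary of Maximum Drug-related Study Drug Injection Site Reaction Adverse Event Grade by Needle Length", for CAB, with Table 3.28 as its RPV counterpart. Both are for the Q2M arm and are listed for the Month 12, Month 26 and end-of-study deliverables, though the last two might not be produced.

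SAP 8.1.1 already links reactions to injections. It states that "ISRs will be assigned based on onset date to the most recent planned IM injection visit prior or equal to the AE onset date", and separately that "ISRs will be attributed to the needle length" when the side of injection allows this. It gives no per-injection denominator. Protocol 6.5.1 permits "Variable needle lengths and/or needles with different gauge" to suit body type, and needle length is recorded in the eCRF.

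**The concern.** A participant has seven injections through Month 12 (Day 1 and Months 2, 4, 6, 8, 10 and 12). One with the ISR is classed by the needle in use at whichever of these preceded the worst reaction. One without it is always classed by the final one. If longer needles become more common over time, the longer-needle group gathers participants without the ISR, and the shorter-needle group gathers those with it. If the trend runs the other way, so does the artefact. If site staff change needle after a reaction, the class follows the outcome directly. At Month 26 there would be 14 injections, so the two reading times could lie further apart.

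These tables exist to show ISR grade by needle length, so a reader will take a gap in them as a needle effect. No listed display reports how many participants changed needle category, so the artefact could not be recognised from the output.

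**Working it through.** The plan states no figure on needle length, so there is nothing of its own to reproduce. The check asks what the rule returns when needle length has no effect on ISRs.

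**Inputs from the documents.** The two-part rule (SAP 5.4.2); seven injections through Month 12 (Protocol 4.2.2 and 8.1.1); needle length may vary, with no rate of change given (Protocol 6.5.1); ISRs occur in most exposed participants, with no rate per injection or per term (Protocol 2.3.1).

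**Assumptions.** Two needle categories, short and long; ISR risk h_v at injection v, the same for both and independent between injections; grades 1/2/3 in the ratio 75/22/3%; the switching patterns below, unrelated to ISRs unless stated.

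**Formula.** The chance that the earliest maximum-grade ISR follows injection v is

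w_v = Σ_g h_v p_g × Π_{u<v}(1 − h_u P(grade ≥ g)) × Π_{u>v}(1 − h_u P(grade > g)).

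Let c = Σ w_v be the share with an ISR, n = 1 − c, and ℓ_v the long-needle share at injection v. Participants with an ISR are read as long with probability a = Σ w_v ℓ_v / c; those without, with probability b = ℓ_7. The table then shows

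- long: ca / (ca + nb)
- short: c(1 − a) / [c(1 − a) + n(1 − b)]

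These agree when a = b and differ otherwise.

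**No switching.** a = b, so both groups show c. At 15% risk, c = 1 − 0.85^7 = 67.9%. The same holds if length varies at random around a constant share.

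**1% switching per injection, 15% risk, 15% starting long.** The weights w_v are 0.126, 0.115, 0.104, 0.095, 0.087, 0.080 and 0.073, so c = 0.6794 and n = 0.3206. The long share rises to b = 1 − 0.85 × 0.99^6 = 0.1997, and a = 0.1169 / 0.6794 = 0.1721.

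- long: 0.1169 / (0.1169 + 0.0640) = 64.6%
- short: 0.5625 / (0.5625 + 0.2566) = 68.7%

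**5% switching per injection, 10% starting long, risk 30% falling by a fifth each time.** c = 0.7349, n = 0.2651, b = 1 − 0.90 × 0.95^6 = 0.3384, a = 0.1719.

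- long: 0.1263 / (0.1263 + 0.0897) = 58.5%
- short: 0.6086 / (0.6086 + 0.1754) = 77.6%

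| ISR risk per injection | Long-needle share, first to seventh injection | Short, any ISR | Long, any ISR | Gap (points) |
|---|---|---|---|---|
| 15% | constant | 67.9% | 67.9% | 0 |
| 15% | 15% to 20% | 68.7% | 64.6% | 4 |
| 15% | 10% to 30% | 71.1% | 57.0% | 14 |
| 15% | 30% to 10% | 65.0% | 81.8% | −17 |
| 30% | 10% to 34% | 93.1% | 86.7% | 6 |
| 30%, falling by a fifth | 10% to 34% | 77.6% | 58.5% | 19 |
| 20% falling to 3% | 30% to 10% | 53.9% | 77.0% | −23 |

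**Switching in response to ISRs.** The formula does not cover this, so it was simulated (400,000 participants, 15% risk, move to the long needle after 30% of ISRs). Any ISR is 67.0% short against 70.7% long; grade 2 or above is 21.6% against 30.0%.

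**Grade cut.** For a very common ISR (60% falling to 20%) with drift from 10% to 30%, any ISR is 98.1% against 95.4%, but grade 2 or above is 51.5% against about 57%. The sign reverses within one table.

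**Alternatives on the same null.** Classing everyone at the first injection makes a = b, so the gap is 0. Within a visit, the per-injection rate is h_v for both lengths. Simulation of the 10%-to-30% drift at 15% risk agrees: 68.0% against 68.2%, and 15.0% against 15.0%.

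**The case against.** A reader might infer that the rule always manufactures differences. The documents do not support that. With a stable needle, or one that varies without trend and without reacting to ISRs, the rule is unbiased. Protocol 6.5.1 recommends one length for most participants and ties longer needles to higher BMI, which suggests stability within a person. The ISR management text in Protocol 8.7.9 does not direct a change of needle. The larger gaps above rest on assumed drift: the 5% pattern takes long-needle use from 10% to 34% with no one switching back.

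Importance is also limited. No objective or endpoint names needle length, SAP 5.4.2 says only that these subgroups may be used, and no test is planned. If all of about 100 participants were in the Q2M arm with 18% on long needles, the standard error of a difference near 68% would be √[0.68 × 0.32 × (1/18 + 1/82)], or 12 points, so a 4-point artefact would be lost in noise. The calculation concerns any ISR, whereas the tables work per term and by grade, and their shells are not shown.

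All of this stands as a limit on size and certainty. It does not remove the defect: nothing in the documents rules out systematic change, and the absence of a test does not protect a percentage from bias.

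**Conclusion.** The flaw is real but conditional. SAP 5.4.2 fixes the time at which needle length is read by whether the participant had the ISR, so Tables 3.24 and 3.28 can show spurious differences when needle length changes systematically over visits or after reactions. In the scenarios run, the gap in any ISR runs from 0 through about 4 points to roughly 20 under strong drift, in either direction. Switching rates, ISR risks and the grade split are all assumptions, because the documents give none of them. It would go too far to say that needle length does drift, or that the planned tables will mislead. The reach is two descriptive Q2M safety tables; no efficacy endpoint is affected. The change is still worth making, because the data needed are already collected.

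**What to change.** In Tables 3.24 and 3.28, make the injection the unit. Within each injection visit and for each preferred term:

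- denominator: CAB (or RPV) injections given with each needle length;
- numerator: those followed by a drug-related ISR assigned to that visit under SAP 8.1.1, by maximum grade;
- a separate 'unknown' row for ISRs whose drug or needle length cannot be attributed.

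Keep the results by visit; a crude pool over visits would mix needle use with any time trend in ISR risk. If a participant-level table is kept, class everyone by needle length at the first injection, delete the last-injection rule for those without an ISR, and report how many participants changed needle category. Footnote that injections within a participant are correlated and that needle choice follows BMI. Neither version removes that confounding. Nor does the per-injection version remove confounding if reaction-prone participants are moved to another needle.

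The cost is revised wording in SAP 5.4.2 and two reprogrammed tables, with no new data. Visit-level cells will be small for the less-used lengths, and the first-injection version loses the link between a reaction and the injection before it.

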## 5.5. Multiple Comparisons and Multiplicity

## 5.5.1. Primary Comparison of Interest

No formal statistical analysis will be performed for this study. The primary endpoint will be summarized based on the ITT-E population.

# 5.6. Other Considerations for Data Analyses and Data Handling Conventions

Other considerations for data analyses and data handling conventions are outlined in the appendices:

Section	Component
12.3	Appendix 3: Assessment Windows
12.4	Appendix 4: Study Phases and Treatment Emergent Adverse Events
12.5	Appendix 5: Data Display Standards & Handling Conventions
12.6	Appendix 6: Derived and Transformed Data
12.7	Appendix 7: Reporting Standards for Missing Data
12.8	Appendix 8: Values of Potential Clinical Importance
12.9	Appendix 9: Snapshot Algorithm Details
12.10	Appendix 10: Identification of Adverse Events of Special Interest

### 6. STUDY POPULATION ANALYSES

#### 6.1. Overview of Planned Study Population Analyses

The study population will be based on the Intent-to-Treat Exposed population, unless otherwise specified.

Study population analyses including analyses of subject's disposition, protocol deviations, demographic and baseline characteristics, prior and concomitant medications, and exposure and treatment compliance will be based on GSK Core Data Standards.

Table 1 provides an overview of the planned study population analyses, with details of the planned displays presented in Appendix 12: List of Data Displays.

Table 1 Overview of Planned Study Population Analyses

Display Type	Data Displays Generated		
	Table	Listing	
Randomization	 		
Randomization [1]		Y [2]	
Subject Disposition			
Study Populations [3]	Υ		
Study Recruitment [3]	Υ	Υ	
Reasons for Screening Failures [3]	Y	Υ	
Rescreened Subjects [3]		Y	
Age Ranges	Y		
Subject Disposition	Y [4][5]		
Reasons for Withdrawal by Visit	Y [4][5]	Y	
IP Discontinuation	Y	Y	
Important Protocol Deviations	Y	Υ	
Deviations leading to exclusion from PP	Y	Y	
Inclusion and Exclusion Criteria Deviations	Y	Y	
Demography and Baseline	·		
Demographics Characteristics	Y	Υ	
Race & Racial Combinations [6]	Y	Υ	
Hepatitis Status	Y		
CDC Classification of HIV infection (2014)	Y		
Distribution of CD4+ Cell Counts at Baseline	Y		
HIV-1 Risk Factors	Y		

Display Type	Data Dis l	olays Generated
	Table	Listing
Medical Conditions, Concomitant Medications & Antiretrov	viral Therapy	
Medical Conditions (Current/Past) [7]	Υ	
Medical Conditions: Sub-conditions (Current/Past) [7,8]	Υ	
Concomitant Medications (non-ART)	Y [9]	
Concomitant Antiretroviral Medications During Maintenance Phase		Υ
ART Medications Received During LTFU Phase		Y
Lipid Modifying Agents (Baseline and During Maintenance Phase)	Y	
Substance use	Υ	
Medical History of Seizure		Y
Other		
Extent of Exposure to IP 	Υ	
Adherence to Injection Dosing Schedule for CAB/RPV 	Υ	

#### NOTES:

- T = Tables, L = Listings, Y = Display Generated,
- 1. All Participants Enrolled population
- 2. Listing of planned and actual treatment.
- 3. All Participants Screened population.
- 4. Subjects who have not been recorded as either completing or withdrawing from the study will be categorized as "Ongoing at time of the analysis" for summary purposes.
- 5. Analysis of subject disposition will be performed for each study phase separately, as well as for overall study conclusion.
- 6. The five high level FDA race categories and designated Asian subcategories will be summarised along with all combinations of high level categories which exist in the data. The nine race categories collected will be summarised along with categories for mixed race. A by-subject listing of race will also be produced.
- 7. Medical conditions will be coded using the Medical Dictionary for Regulatory Activities (MedDRA).
- 8. Sub conditions are Cardiovascular, Gastrointestinal, Metabolism and Nutrition, Psychiatric, Renal and Urinary, Nervous System Conditions and Hepatobiliary
- 9. Summarised by Ingredient ATC Level 1, Ingredient combinations and Combination term ATC Level 1 (EG Includes single-ingredient medications with multi-ingredient medications labeled according to the sum of their ingredients, e.g., "TYLENOL Cold and Flu" would appear as "CHLORPHENAMINE MALEATE + DEXTROMETHORPHAN HYDROBROMIDE + PARACETAMOL + PSEUDOEPHEDRINE HYDROCHLORIDE" under the ATC headings for "Nervous System" and "Respiratory System" (the combination's ATC classifications).)
- 10. Safety Population

#### 6.2. Prior and Concomitant Medications

Non-ART and/or ART Medications will be classified by categories shown in Table 2. The same medication may be classified by more than one category. For example, if the Non-ART medication was started prior to the Maintenance treatment start date and was stopped at Month 6 while subject was still receiving study treatment, this medication would be considered both 'prior' and 'concomitant during maintenance'.

Table 2 Derived Data for Non-ART Medications/ART Medications

	Definition
Prior	ART Medication Taken ≤ Maintenance Treatment Start Date
	Non-ART Medication Taken < Maintenance Treatment Start Date
Concomitant during	Maintenance Treatment Start Date ≤ Non-ART Medication Taken < LTFU
Maintenance	ART Start Date
	Maintenance Treatment Start Date < ART Medication Taken < LTFU ART
	Start Date
Received during	For subjects Who received at least one CAB and/or RPV injection and
Long-term Follow-up	have started LTFU ART:
	Non-ART/ART Medication Taken ≥ LTFU ART Start Date

#### NOTES:

- Please refer to Appendix 7: Reporting Standards for Missing Data for handling of missing and partial dates for medications. Use the rules in this table if medication date is completely missing.
- If subjects have missing LFTU ART start date, only the lower bound will be considered in the derivation.

#### 7. EFFICACY ANALYSES

## 7.1. Primary Efficacy Analyses

No formal statistical analysis will be performed for the primary endpoint of the study.

